- Return to baseline PS
- Baseline +3 cmH₂O
- Baseline +6 cmH₂O

The order of the four non-baseline steps will be randomized for each patient using sealed envelopes, while the baseline PS step will be performed first and repeated last to assess measurement reproducibility.

At each pressure support (PS) level, a 2-minute stabilization period will be followed by three consecutive measurements of the following parameters: tidal volume (V_t), respiratory rate, P_{0.1}, P_{occ}, pressure muscle index (PMI), static compliance of the

respiratory system (Crs), and peripheral oxygen saturation (SpO_2). Vt , RR , P0.1 , Pocc , PMI , and Crs will be obtained from the ventilator, while SpO_2 will be recorded from the ICU monitor. PMI will be calculated as $\text{PMI} = \text{Pplat} - (\text{PEEP} + \text{PS})$, and Crs as $\text{Crs} = \text{Crs} = \text{Vt} / (\text{Pplat} - \text{PEEP})$. All values will be averaged across the three readings. **Figure 1. Study**

Protocol Flowchart

Measurements and Outcomes

Primary Outcome

- To evaluate changes in respiratory drive and inspiratory effort—quantified using P0.1, maximum negative occlusion pressure (Pocc), and pressure muscle index (PMI)—across varying levels of pressure support in adult surgical ICU patients after major abdominal surgery.

Secondary Outcomes

- To quantify the incidence of quasi-passive and active response patterns during pressure support ventilation, based on physiological criteria derived from patient responses.
- To assess the relationship between these ventilatory response patterns and clinical outcomes, including duration of mechanical ventilation, ICU length of stay, reintubation or non-invasive ventilation use, and ICU/hospital discharge disposition.

Definition of ventilatory response patterns:

- An active pattern is characterized by relatively stable V_t and plateau pressure despite reductions in pressure support, accompanied by a compensatory increase in PMI—indicating greater patient-driven effort. In contrast, a quasi-passive pattern is marked by a progressive decline in V_t and plateau pressure with little or no change in PMI, suggesting limited patient contribution to ventilation. ⁽⁷⁾
- As no standardized thresholds currently exist, these classifications will be determined post hoc based on individual response trends observed in the study dataset.

Data Collection

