All data will be prospectively collected during each predefined pressure support (PS) level (baseline, ± 3 cmH₂O, ± 6 cmH₂O), following a 2-minute stabilization period at each step. The following variables will be recorded:

1. Demographics and Baseline Clinical Data

- Age, sex, height, weight, BMI
- Primary diagnosis and operation
- APACHE II or SOFA score at ICU admission
- Time from intubation to enrollment (hours)
- Baseline ventilator settings (PEEP, FiO₂, baseline PS)
- Baseline arterial blood gas (ABG): pH, PaCO₂, PaO₂, HCO₃⁻, SaO₂

2. Ventilatory and Physiological Parameters (at each PS level)

- Tidal volume (Vt) – measured from ventilator display
- Respiratory rate – measured from ventilator
- Minute ventilation (MV) – calculated
- P_{0.1} – occlusion pressure at 0.1 seconds
- P_{occ} – airway pressure drop during inspiratory hold
- PMI – pressure muscle index calculated as P_{plat} – (PEEP + PS)
- P_{plat} – plateau pressure (via inspiratory hold)
- P_{peak} – peak inspiratory pressure
- Crs – static compliance: Vt / (P_{plat} – PEEP)
- SpO₂ – peripheral oxygen saturation (pulse oximetry)
- EtCO₂ – end-tidal CO₂ if available
- HR and MAP – heart rate and mean arterial pressure (non-invasive or arterial line)
- Use of accessory muscles – observational note
- Signs of distress or dyssynchrony – e.g., paradoxical breathing, anxiety, diaphoresis

4. Post-Protocol Clinical Follow-up

- Duration of mechanical ventilation after study (in hours)
- Need for reintubation or non-invasive ventilation within 48 h
- Total ICU length of stay (LOS)
- ICU and hospital discharge status
- Complications: VAP, barotrauma, unexpected weaning failure

Safety and Tolerability

The protocol allows immediate cessation of PS level changes and return to baseline settings if any of the following occur:

- Respiratory rate >35 breaths/min
- SpO₂ < 90%
- HR > 140 bpm or >30% change from baseline
- Signs of distress: diaphoresis, agitation, anxiety
- Hemodynamic instability

Sample Size

This is an exploratory physiological study using a repeated-measures design. Based on prior literature (Docci et al., 2023; Umbrello et al., 2015), a within-subject difference in

the pressure muscle index (PMI) of approximately 2.0 cmH₂O (standard deviation ~2.5) between pressure support (PS) levels is considered clinically meaningful.

Using a two-sided paired t-test with the following assumptions:

- Alpha (α) = 0.05
- Power (1 - β) = 0.90
- Effect size = 0.8

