The calculated minimum required sample size is 20 patients. To improve the precision of subgroup analyses, enhance generalizability, and account for possible dropouts or incomplete data, we plan to enroll a total of 40 patients.

Statistical Analysis

Descriptive statistics will be used to summarize baseline characteristics. Continuous variables will be presented as mean \pm standard deviation or median (IQR), depending on distribution. Categorical variables will be summarized as counts and percentages.

Primary analysis:

- Repeated-measures ANOVA or Friedman test (non-parametric) will be used to assess changes in PMI, Pocc, and P0.1 across PS levels.
- Post-hoc pairwise comparisons will be performed with Bonferroni correction.

Secondary analysis:

- Pearson or Spearman correlation will be used to evaluate relationships between effort indices (PMI, Pocc, P0.1).
- Linear mixed models will explore associations between PS levels and effort parameters, accounting for intra-patient variability.
- The incidence of under- and over-assistance will be described, and logistic regression may be used to assess their associations with clinical outcomes (e.g., prolonged ventilation).

A p-value <0.05 will be considered statistically significant. Statistical analyses will be performed using R.

Ethical Considerations

- Study protocol to be approved by institutional ethics board.
- Written informed consent obtained from patient or surrogate.
- Minimal risk as PS level adjustments are brief and within clinically accepted ranges.

References

1. van Oosten JP, Akoumianaki E, Jonkman AH. Monitoring respiratory muscles effort during mechanical ventilation. *Curr Opin Crit Care*. Feb 1 2025;31(1):12-20. doi:10.1097/mcc.0000000000001229

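### The first-to-last baseline difference cannot by itself show measurement reproducibility, because it combines measurement error with session drift and any residual effect of the preceding pressure support step

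*Protocol*

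**What the plan says.** All of the design text is in the protocol, under Pressure Support Steps. The four non-baseline levels (baseline -6, -3, +3 and +6 cmH2O) are taken in an order randomized for each patient by sealed envelope, "while the baseline PS step will be performed first and repeated last to assess measurement reproducibility". At each level, "a 2-minute stabilization period will be followed by three consecutive measurements of the following parameters", and "All values will be averaged across the three readings". No return to baseline between the randomized steps is stated.

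The bulleted list just above that sentence gives a different order: baseline, -6, -3, return to baseline, +3, +6. There the repeat baseline is fourth of six, not last.

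Under Statistical Analysis, the primary analysis compares PMI, Pocc and P0.1 across PS levels by repeated-measures ANOVA or the Friedman test. Among the secondary analyses, "Linear mixed models will explore associations between PS levels and effort parameters, accounting for intra-patient variability".

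The document gives no figure for carry-over, for drift or for measurement error.

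**The concern.** A repeat measurement isolates measurement error only if nothing else has changed between the two occasions. Here four changes of pressure support and the length of the session lie between the two baselines, and the step just before the second one varies by patient. Slow adjustment, or a patient who tires or wakes, would appear in the same number as instrument noise. Sound measurements could then be reported as poorly reproducible, or a real physiological lag could be dismissed as noise.

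The repeat baseline is also the design's only built-in check on whether 2 minutes is long enough. Labelling it a reproducibility measure gives that check a different purpose. This matters because randomizing the order does not cancel carry-over in the comparison of PS levels. If there is any, it pulls the levels towards each other, and the primary outcome concerns how effort changes across those levels.

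**Working it through.** **The plan's own figure.** The protocol gives no number on this point. Its sample size is used below to gauge the effect on power. The inputs under Sample Size are "Using a two-sided paired t-test with the following assumptions", "Alpha (α) = 0.05", "Power (1 - β) = 0.90" and "Effect size = 0.8" (2.0/2.5). The exact paired t-test needs n = 19 (power 0.909); at the stated minimum of 20 the power is 0.924. The figure reproduces.

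**What the baseline difference contains.** Let s be the change in PMI per cmH2O of PS, c the fraction of the previous step's effect still present at reading, and p the level of the last randomized step relative to baseline. For one session,

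last - first = drift + c·s·p + (error_last - error_first).

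This is one number with three sources. The decomposition needs no assumed size for c.

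**Carry-over at the last baseline.** p is -6, -3, +3 or +6 with probability 1/4 each. Its mean is 0 and its SD is √((36 + 9 + 9 + 36)/4) = √22.5 = 4.74. Carry-over therefore adds spread across patients and no mean shift. The protocol does not say which pair of PS levels its 2.0 cmH2O refers to, so s is assumed at two extremes. At c = 0.2 (assumed):

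- 2.0 per 3 cmH2O: 0.2 × 0.667 × 4.74 = 0.63 cmH2O.
- 2.0 per 12 cmH2O: 0.2 × 0.167 × 4.74 = 0.16 cmH2O.
- If carry-over accumulates over successive steps instead of coming only from the last one, enumerating all 24 orders gives an SD of 0.71 cmH2O of PS. At the steep slope that is 0.71 × 0.667 = 0.47 cmH2O of PMI.

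The apparent test-retest SD, without drift, is √(σ² + SD²/2), where σ is the measurement SD of a step mean. Neither σ = 0.5 nor σ = 1.0 is in the protocol.

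- Steep slope, σ = 0.5: √(0.25 + 0.20) = 0.67, or 34% too high.
- Steep slope, accumulating, σ = 0.5: √(0.25 + 0.11) = 0.60, or 20% too high.
- Flat slope, σ = 1.0: √(1 + 0.0125) = 1.006, or under 1% too high.

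**Carry-over in the PS contrasts.** A level x comes directly after the first baseline with probability 1/4. Otherwise it follows one of the other three levels, equally often, and those sum to -x. The mean preceding level is (3/4)(-x/3) = -x/4, so -6 follows +1.5 on average and +6 follows -1.5. With observed level = x + c(previous - x), the mean is x(1 - 1.25c):

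| c (assumed) | mean at -6 / +6 | shrinkage |
|---|---|---|
| 0 | -6.00 / +6.00 | 0% |
| 0.1 | -5.25 / +5.25 | 12.5% |
| 0.2 | -4.50 / +4.50 | 25% |
| 0.3 | -3.75 / +3.75 | 37.5% |

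The accumulating model gives nearly the same factors: 0.88, 0.75 and 0.64 at c = 0.1, 0.2 and 0.3. With those factors and the SD held at 2.5, power at the planned 40 patients is 0.991, 0.961 and 0.88.

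**Cost of adjusting if c = 0.** Take preceding level as a linear term, with 0 entered for the first step. Per patient its sum of squares is 36 + 9 + 9 + 36 = 90. Differences between level means account for 2(1.5² + 0.75²) = 5.625, leaving 84.375. The +6 and -6 means of this term differ by 3. With patient effects and balanced orders, the variance of the -6 versus +6 contrast rises from 2σ²/n to (2 + 9/84.375)σ²/n, a ratio of 1.053. A linear position term adds nothing to this contrast when positions are balanced. Unbalanced random lists cost about 1% more.

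Categorical position is not usable. Baseline occupies only positions 1 and 6, so with 40 patients the design matrix has rank 49 for 50 columns.

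**The case against.** The strongest reply is that the protocol does guard against carry-over, with 2 minutes at each step before any reading, and that nothing in it shows this is too short. That stands. A reader might infer that the primary contrasts are attenuated, or that the stabilization period is inadequate. The document supports neither: c may be 0, in which case there is neither shrinkage nor added spread. In patients with a quasi-passive pattern, whose PMI by definition hardly changes with PS, carry-over in PMI would be close to nil.

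Secondly, returning to a setting and measuring again is an ordinary test-retest check, and consecutive readings at a fixed setting capture something narrower. This is fair as to terms. It does not rescue the stated purpose, because a test-retest difference taken after varying steps still does not isolate the measurement.

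Thirdly, covariate terms in a secondary model are commonly left to the SAP, which is not at hand. That also stands, so their absence is no defect here and the terms are offered only as a recommendation. Likewise, averaging the three readings does not mean that the individual values are discarded.

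Fourthly, a reader might expect balanced step orders, such as a Williams square, to remove the shrinkage. They would not: the mean preceding level of -6 and +6 is again +1.5 and -1.5.

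Power is a partial answer only. It stays at about 0.88 or higher over the assumed range, but shrinkage would bias the estimated size of change at any sample size.

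**Conclusion.** The point holds as a matter of design logic. Under the sentence that places it last, the repeat baseline measures return to baseline, which is error plus drift plus any carry-over. It cannot by itself show measurement reproducibility.

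The size is unknown and conditional. Over an assumed c of 0 to 0.3, contrasts between non-baseline levels would shrink by 0% to about 37.5% (about 25% at c = 0.2), given a response linear in PS. At the last baseline the mean effect is zero, and at c = 0.2 the added SD is about 0.16 to 0.63 cmH2O of PMI across the two assumed slopes, or about 0.47 at the steep slope if carry-over accumulates. None of these figures shows that carry-over exists.

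The calculations apply to the randomized order only. Under the listed sequence the repeat baseline always follows -3, so a residual effect would have the same direction in every patient. It would still be mixed with drift and error. The two statements of the order contradict each other and must be reconciled. This is a cheap improvement to make before enrolment, not a flaw that invalidates the study.

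**What to change.** 1. Keep the three individual readings at each step in the dataset and estimate within-step repeatability from them (within-step SD or ICC), alongside the step means used in the main analysis.
2. Restate the first-versus-last baseline comparison as a return-to-baseline check, and analyse it against the level of the step just before it. The slope on that level then indicates carry-over and the intercept mean drift.
3. As a sensitivity analysis of the PS contrasts, add preceding PS level (linear) and step position (linear, not categorical) to the planned mixed model.
4. Reconcile the listed sequence, with return to baseline fourth, with the sentence that puts the repeat baseline last.

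No extra measurements are needed. The cost is protocol wording, retention of the raw readings, and about 5% more variance in the -6 versus +6 contrast in the sensitivity model if there is no carry-over. A balanced envelope list is optional and adds little: about 1% in precision, with no change in the shrinkage.

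### Three unranked primary indices are each tested at 0.05, with no rule for combining them: the any-of-three false-positive chance is about 14% if independent, about 9% at an assumed correlation of 0.9

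*Protocol*

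**What the plan says.** Under Measurements and Outcomes, the Primary Outcome is the change in respiratory drive and inspiratory effort across pressure support levels, "quantified using P0.1, maximum negative occlusion pressure (Pocc), and pressure muscle index (PMI". No index is placed above the others, and no rule says whether one, some or all of them must change.

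Under Statistical Analysis, the primary analysis reads: "Repeated-measures ANOVA or Friedman test (non-parametric) will be used to assess changes in PMI, Pocc, and P0.1 across PS levels". That is one omnibus test per index, three in all. The next line is "Post-hoc pairwise comparisons will be performed with Bonferroni correction". The section's only threshold is general: "A p-value <0.05 will be considered statistically significant".

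The Sample Size section plans on a within-patient PMI difference of about 2.0 cmH₂O with an SD of about 2.5, which "between pressure support (PS) levels is considered clinically meaningful". It uses a two-sided paired t-test with "Alpha (α) = 0.05" and "Power (1 - β) = 0.90". It gives a minimum of 20 patients and plans to enrol 40. No difference or SD is given for Pocc or P0.1. The same section calls the study exploratory.

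**The concern.** With three primary tests, each at 0.05, and no rule for reading them together, the protocol leaves open what counts as a primary result. A report could present whichever index falls below 0.05 as the primary finding. Under that reading the chance of at least one false primary finding is above 0.05. The stated Bonferroni correction does not deal with this, because it is attached to the pairwise comparisons after the omnibus tests.

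The plan therefore controls error among pairwise contrasts but not one level up, among the indices. A reader could also take the power statement to cover the whole primary outcome, when its inputs are for PMI alone.

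**Working it through.** **1. Reproduce the protocol's own figure.** Effect size d = 2.0/2.5 = 0.8, two-sided alpha 0.05, paired t-test, noncentrality 0.8·√n.
- n = 19: noncentrality 3.49, power 0.909. This is the smallest n that reaches 0.90.
- n = 20: noncentrality 3.58, power 0.924.

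The stated minimum of 20 is sound for its inputs.

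**2. Any-of-three error when no index changes.** Inputs: three tests at 0.05, from the Primary Outcome and Statistical Analysis sections. For independent tests, 1 − (1 − 0.05)³ = 1 − 0.857 = 0.143.

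The indices come from the same patients, so some correlation is likely, but the document gives none. The values below are assumptions. The simulation used repeated-measures ANOVA with 40 patients, five pressure support levels, equal correlation among the indices, spherical errors, no effect on any index, and 20,000 simulated trials per row.

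| Assumed correlation | Chance that at least one of three has p<0.05 |
|---|---|
| 0 | 14.1% |
| 0.3 | 13.5% |
| 0.5 | 12.3% |
| 0.7 | 11.2% |
| 0.8 | 9.9% |
| 0.9 | 9.0% |
| 0.95 | 7.6% |

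Using six steps, or 20 patients, changes these by less than one percentage point. Each single test stays close to 5%, so the excess comes from having three of them.

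**3. Error when PMI truly changes and the other two do not.** For the two remaining tests, 1 − 0.95² = 0.0975 if independent, and less if they are correlated.

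**4. Error under Holm.** The ordered p-values are compared with 0.05/3 = 0.0167, then 0.05/2 = 0.025, then 0.05.
- No index changes: an error needs the smallest p-value to be below 0.0167. If independent, 1 − (1 − 0.0167)³ = 0.049.
- Only PMI changes and is detected: the other two start at 0.025. If independent, 1 − 0.975² = 0.049.

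Holm keeps the error at or below 0.05 whatever the correlation.

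**5. Power cost for PMI at the strictest step, alpha 0.0167, d = 0.8.**
- n = 20: power 0.818.
- n = 25: the smallest n with power of at least 0.90.
- n = 40: power 0.993.

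These figures use the protocol's own paired comparison as the yardstick, not the omnibus test. For Pocc and P0.1 no calculation is possible, because the document gives no difference and no SD.

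**The case against.** *The study is exploratory.* It claims neither familywise error control nor confirmatory efficacy, and many would report three complementary physiological measures without adjustment. This stands as a reason to rate the point low. It does not remove the point, because the protocol sets a significance threshold, a power target and a Bonferroni rule, and so has chosen to control error at the level below.

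*No success rule means no inflated error.* A reader might infer that this trial's chance of a false primary finding simply is 9 to 14% instead of 5%. The document does not support that. The figure needs an any-one-counts reading, no effect of pressure support on any index, and an assumed correlation. If all three indices had to change, the error would not exceed 5%. The protocol also plans on PMI changing, so no effect on any index is far from its own premise. The case in which only PMI changes is closer to that premise, and the error is still up to 9.75% there.

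*The analysis plan may settle it.* Allocation of alpha is often left to that document, which is not shown, and the family for the Bonferroni correction is not spelled out. This is a fair limit. The protocol itself, however, fixes three equal primary indices and writes its own multiplicity rule, and on its plain wording that rule concerns pairwise contrasts.

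*The power statement is wrong.* A reader might infer this too. It is not: the 90% is tied to PMI and is correct for PMI. Power for Pocc and P0.1 is unknown, which is not the same as inadequate.

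*Naming PMI as the single primary outcome would be simpler.* It would, but the Background section assigns P0.1 to drive, and Pocc and PMI to effort. That choice would drop drive from a primary objective that covers both.

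**Conclusion.** The point holds as a minor one. The primary outcome has three unranked indices, each tested at 0.05, with no adjustment stated across them and no rule for combining the results. If a change in any one is taken as a primary finding and none truly changes, the chance of a false finding is about 14% for independent indices and about 9% at an assumed correlation of 0.9; above that it falls further. If PMI alone truly changes, the chance for the other two is at most 9.75%, reached when they are independent. There is no error in the sample size: 20 is adequate for the PMI comparison as specified, and 40 are planned.

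**What to change.** Keep P0.1, Pocc and PMI as the primary indices. In Statistical Analysis, state that the three omnibus p-values will be adjusted by Holm, that an index is declared changed only if its adjusted p-value is below 0.05, and that the Bonferroni-corrected pairwise comparisons are made within each index. In Sample Size, state that the calculation is for PMI only and that power for Pocc and P0.1 was not calculated.

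The cost is a few sentences, with no further patients or measurements. The omnibus tests become slightly stricter, with thresholds from 0.0167 to 0.05. For PMI the loss is negligible if all 40 patients contribute data. If only 20 did, power at the strictest step would be 0.818. The loss for Pocc and P0.1 cannot be quantified from the document.

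### Death shortens ventilation hours and ICU stay as defined, so their comparison between response patterns is biased and can reverse if mortality differs clearly

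*Protocol*

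**What the plan says.** Under Secondary Outcomes, the protocol will assess how the active and quasi-passive patterns relate to "clinical outcomes, including duration of mechanical ventilation, ICU length of stay, reintubation or non-invasive ventilation use, and ICU/hospital discharge disposition".

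Data Collection, item 4 (Post-Protocol Clinical Follow-up) sets the variables:
- ventilation, in hours, counted after the study;
- "Need for reintubation or non-invasive ventilation within 48 h", with no stated start for the 48 hours and no stated group at risk;
- "Total ICU length of stay (LOS", that is, a total with no later starting point;
- ICU and hospital discharge status, as a separate item.

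Statistical Analysis says only that logistic regression may be used for associations with clinical outcomes. Its one example is prolonged ventilation, without a cut-off. Nothing links discharge status to the other three items. Dates of extubation, ICU discharge and death are not on the list.

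**The concern.** Ventilation time and ICU stay end at death as well as at recovery. A death on the ventilator two days after the session and a successful extubation at two days give the same number of ventilated hours. If one response pattern carries higher mortality, its durations are shortened for the wrong reason, and the pattern can look neutral or even favourable.

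The clocks also differ. Ventilation is counted from the study, ICU stay is a total, and the 48-hour item has no written origin. Inclusion requires more than 48 hours of invasive ventilation, so total ICU stay contains part or all of that earlier period, depending on where ventilation began. The measured pattern cannot have influenced that time, although longer earlier ventilation might influence the pattern.

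At stake is whether the pattern-outcome results can be read in the direction in which they are reported.

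**Working it through.** **The plan's own figure.** The only calculated figure is the sample size: "The calculated minimum required sample size is 20 patients". With d = 2.0/2.5 = 0.8, two-sided alpha 0.05 and power 0.90, the exact paired t-test needs 19 patients, and 20 give power 0.924. The figure reproduces. It concerns the pressure muscle index and does not bear on this point.

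**Inputs for the check.** The protocol gives no extubation, death or reintubation rates and no cut-off for prolonged ventilation. All of these are assumptions here. The cut-off is set at 7 days.

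**Model for duration.** Constant daily hazards: e for extubation, m for death on the ventilator.
- Mean ventilated time = 1/(e + m)
- P(ventilated beyond 7 days) = exp(−7(e + m)), where a death before day 7 counts as not prolonged
- P(not extubated alive by day 7) = 1 − [e/(e + m)] × [1 − exp(−7(e + m))], where death counts as failure

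Pattern A has e = 0.20, m = 0.02:
- mean = 1/0.22 = 4.55 days
- P(beyond 7 days) = exp(−1.54) = 0.214
- P(not extubated alive by day 7) = 1 − 0.909 × 0.786 = 0.286

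Pattern B is worse on both hazards in every row. Odds ratios are B against A.

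| B: e, m | Die on ventilator, A / B | Mean days, B | P(>7 d), B | OR, duration as written | P(not extubated alive by day 7), B | OR, death as failure |
|---|---|---|---|---|---|---|
| 0.15, 0.03 | 9% / 17% | 5.56 | 0.284 | 1.45 | 0.403 | 1.69 |
| 0.15, 0.05 | 9% / 25% | 5.00 | 0.247 | 1.20 | 0.435 | 1.92 |
| 0.15, 0.08 | 9% / 35% | 4.35 | 0.200 | 0.92 | 0.478 | 2.29 |
| 0.16, 0.10 | 9% / 38% | 3.85 | 0.162 | 0.71 | 0.484 | 2.35 |

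Last row in full: (0.162/0.838)/(0.214/0.786) = 0.71, against (0.484/0.516)/(0.286/0.714) = 2.35. The first two rows show attenuation, the last two reversal.

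**A small example.** Of 15 quasi-passive patients, 5 die at 2 days and 10 are extubated at 6 days: mean (5×2 + 10×6)/15 = 4.7 days. The other 25 are all extubated alive at 5 days. The group with 5/15 = 33% mortality has the shorter mean. The medians, however, are 6 and 5 days, so the summary chosen decides the direction. A cut-off between 5 and 6 days gives 10/15 against 0/25 prolonged (quasi-passive worse). One between 2 and 5 days gives 10/15 against 25/25 (quasi-passive better).

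**Reintubation or NIV, if counted over all enrolled.** Risk = (1 − share never extubated) × risk among those extubated.
- 10% against 40% never extubated, risks 20% and 25%: 0.90 × 0.20 = 18% against 0.60 × 0.25 = 15%, reversed.
- 5% against 10% never extubated, same risks: 0.95 × 0.20 = 19% against 0.90 × 0.25 = 22.5%, not reversed.

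**The case against.** The follow-up list is a data-collection list. The protocol has no rule that counts death as a good result. Handling of death and denominators is often left to a statistical analysis plan, which may exist but was not available. Death is not hidden: discharge disposition is itself a named outcome, and in the small example 5/15 against 0/25 deaths gives Fisher's exact p = 0.005. Unexpected weaning failure is recorded as a complication. Hours from intubation to enrolment are also recorded, so prior ventilation can be adjusted for, and ventilation duration already excludes time before the study.

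Most of this stands and limits the point. It does not remove it. The two durations and the total time origin are set in the protocol, and a later analysis can repair them only if the dates are recorded.

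A reader might infer three stronger things, none of which the protocol supports:
- *Patients who stay intubated are scored as doing well.* They accrue long ventilation and a long stay. Only the reintubation/NIV item could read as event-free for them, and only over all enrolled patients.
- *The 48 hours run from the end of the protocol sessions, so a patient still intubated cannot have the event.* The section title allows this, but reintubation presupposes extubation, which is the natural start. The gap is an unwritten anchor.
- *A given number of patients is misranked*, for instance 4 to 12 of 40 at an assumed ICU mortality of 10 to 30%. That would need every ICU death to be an early death on the ventilator. Deaths after long ventilation are not scored as short, and enrolment selects stable patients.

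**Conclusion.** The point holds for the two durations. As written, they are cut short by death, which biases the comparison between response patterns. Under the assumed hazards the distortion runs from slight attenuation (1.45 instead of 1.69) to reversal (0.71 instead of 2.35). Reversal occurred in the scenarios where about 35% or more of one pattern, against 9% of the other, die on the ventilator. The direction in real data also depends on the summary and cut-off used, and the protocol gives no figure from which to say which case applies. Separately, total ICU stay includes time that precedes the measurement.

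The weight is moderate. The Background section places the association within the second of two primary objectives, but as something to explore. It is listed as a secondary outcome, and its regression is optional. The primary physiological outcome is unaffected.

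**What to change.** 1. Add dates and times of extubation, ICU discharge and death to the follow-up list.
2. Replace post-study ventilation hours by time from the first session to extubation alive, with death as a competing event. Ventilator-free days to day 28 with death counted as 0 would also serve, but only if day-28 status is obtained, which the list does not now provide.
3. Replace total ICU stay by time from the first session to ICU discharge alive, with death as a competing event.
4. Define reintubation or NIV as occurring within 48 hours of first extubation, among extubated patients. Report death and non-extubation separately by pattern.

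The cost is three chart dates per patient, a few lines of outcome wording, and results slightly less intuitive than hours or days. No change to the measurement sessions or sample size is needed.
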